17.2. Regulatory Documentation

17.2.1. Regulatory Approval/Notification

This protocol and any amendment(s) must be submitted to the appropriate regulatory authorities in each respective country, if applicable. A study may not be initiated until all local regulatory requirements are met.

17.2.2. Required Prestudy Documentation

The following documents must be provided to the sponsor before shipment of study drug to the study site:

- Protocol and amendment(s), if any, signed and dated by the principal investigator
- A copy of the dated and signed (or sealed, where appropriate per local regulations), written IEC/IRB approval of the protocol, amendments, ICF, any recruiting materials, and if applicable, subject compensation programs. This approval must clearly identify the specific protocol by title and number and must be signed (or sealed, where appropriate per local regulations) by the chairman or authorized designee.
- Name and address of the IEC/IRB, including a current list of the IEC/IRB members and their function, with a statement that it is organized and operates according to GCP and the applicable laws and regulations. If accompanied by a letter of explanation, or equivalent, from the IEC/IRB, a general statement may be substituted for this list. If an investigator or a member of the study-site personnel is a member of the IEC/IRB, documentation must be obtained to state that this person did not participate in the deliberations or in the vote/opinion of the study.
- Regulatory authority approval or notification, if applicable
- Signed and dated statement of investigator (eg, Form FDA 1572), if applicable
- Documentation of investigator qualifications (eg, curriculum vitae)
- Completed investigator financial disclosure form from the principal investigator, where required
- Signed and dated clinical study agreement, which includes the financial agreement
- Any other documentation required by local regulations

The following documents must be provided to the sponsor before enrollment of the first subject:

- Completed investigator financial disclosure forms from all subinvestigators
- Documentation of subinvestigator qualifications (eg, curriculum vitae)
- Name and address of any local laboratory conducting tests for the study, and a dated copy of current laboratory normal ranges for these tests, if applicable
- Local laboratory documentation demonstrating competence and test reliability (eg, accreditation/license), if applicable

17.3. Subject Identification, Enrollment, and Screening Logs

The investigator agrees to complete a subject identification and enrollment log to permit easy identification of each subject during and after the study. This document will be reviewed by the sponsor study-site contact for completeness.

The subject identification and enrollment log will be treated as confidential and will be filed by the investigator in the study file. To ensure subject confidentiality, no copy will be made. All reports and communications relating to the study will identify subjects by subject identification and date of birth. In cases where the subject is not enrolled into the study, the date seen and date of birth will be used.

The investigator must also complete a subject screening log, which reports on all subjects who were seen to determine eligibility for inclusion in the study.

17.4. Source Documentation

At a minimum, source documentations consistent in the type and level of detail with that commonly recorded at the study site as a basis for standard medical care, must be available for the following: subject identification, eligibility, and study identification; study discussion and date of signed informed consent/assent; dates of visits; results of safety and efficacy parameters as required by the protocol; record of all adverse events and follow-up of adverse events; concomitant medication; drug receipt/dispensing/return records; study drug administration information; and date of study completion and reason for early discontinuation of study drug or withdrawal from the study, if applicable.

The author of an entry in the source documents should be identifiable.

Specific details required as source data for the study and source data collection methods will be reviewed with the investigator before the study and will be described in the monitoring guidelines (or other equivalent document).

Inclusion and exclusion criteria not requiring documented medical history must be verified at a minimum by parent/legally acceptable representative interview or other protocol required assessment (eg, physical examination, laboratory assessment) and documented in the source documents.

An electronic source system may be utilized, which contains data traditionally maintained in a hospital or clinic record to document medical care (eg, electronic source documents) as well as the clinical study-specific data fields as determined by the protocol. This data is electronically extracted for use by the sponsor. If the electronic source system is utilized, references made to the eCRF in the protocol include the electronic source system but information collected through the electronic source system may not be limited to that found in the eCRF. Data in this system may be considered source documentation.

17.5. Case Report Form Completion

Case report forms are prepared and provided by the sponsor for each subject in electronic format. All data relating to the study must be recorded in eCRF. All eCRF entries, corrections, and alterations must be made by the investigator or authorized study-site personnel. The investigator must verify that all data entries in the eCRF are accurate and correct.

Electronic data capture will be used for this study. The study data will be transcribed by study-site personnel from the source documents onto an electronic eCRF, if applicable. Study-specific data will be transmitted in a secure manner to the sponsor.

Worksheets may be used for the capture of some data to facilitate completion of the eCRF. Any such worksheets will become part of the subject's source documentation. All data relating to the study must be recorded in eCRFs prepared by the sponsor. Data must be entered into eCRFs in English. The eCRF must be completed as soon as possible after a subject visit, and the forms should be available for review at the next scheduled monitoring visit.

The investigator must verify that all data entries in the eCRFs are accurate and correct.

All eCRF entries, corrections, and alterations must be made by the investigator or other authorized study-site personnel. If necessary, queries will be generated in the eDC tool.

If necessary, queries will be generated in the eDC tool. If corrections to a eCRF are needed after the initial entry into the eCRF, this can be done either of the following ways:

- Investigator and study site personnel can make corrections in the eDC tool at their own initiative or as a response to an auto query (generated by the eDC tool)
- Sponsor or sponsor delegate can generate a query for resolution by the investigator and study-site personnel.

17.6. Data Quality Assurance/Quality Control

Steps to be taken to ensure the accuracy and reliability of data include the selection of qualified investigators and appropriate study sites, review of protocol procedures with the investigator and study-site personnel before the study, and periodic monitoring visits by the sponsor, and direct transmission of clinical laboratory data from a central laboratory into the sponsor's data base. Written instructions will be provided for collection, handling, storage, and shipment of samples.

Guidelines for eCRF completion will be provided and reviewed with study-site personnel before the start of the study.

The sponsor will review eCRFs for accuracy and completeness during on-site monitoring visits and after transmission to the sponsor; any discrepancies will be resolved with the investigator or designee, as appropriate. After upload of the data into the study database they will be verified for accuracy and consistency with the data sources.

17.7. Record Retention

In compliance with the ICH/GCP guidelines, the investigator/institution will maintain all eCRFs and all source documents that support the data collected from each subject, as well as all study documents as specified in ICH/GCP Section 8, Essential Documents for the Conduct of a Clinical Trial, and all study documents as specified by the applicable regulatory requirement(s). The investigator/institution will take measures to prevent accidental or premature destruction of these documents.

Essential documents must be retained until at least 2 years after the last approval of a marketing application in an ICH region and until there are no pending or contemplated marketing applications in an ICH region or until at least 2 years have elapsed since the formal discontinuation of clinical development of the investigational product. These documents will be retained for a longer period if required by the applicable regulatory requirements or by an agreement with the sponsor. It is the responsibility of the sponsor to inform the investigator/institution as to when these documents no longer need to be retained.

If the responsible investigator retires, relocates, or for other reasons withdraws from the responsibility of keeping the study records, custody must be transferred to a person who will accept the responsibility. The sponsor must be notified in writing of the name and address of the new custodian. Under no circumstance shall the investigator relocate or dispose of any study documents before having obtained written approval from the sponsor.

If it becomes necessary for the sponsor or the appropriate regulatory authority to review any documentation relating to this study, the investigator/institution must permit access to such reports.

17.8. Monitoring

The sponsor will use a combination of monitoring techniques, central, remote, or on-site monitoring, to monitor this study. The sponsor will perform on-site monitoring visits as frequently as necessary. The monitor will record dates of the visits in a study site visit log that will be kept at the study site. The first post-initiation visit will be made as soon as possible after enrollment has begun. At these visits, the monitor will compare data entered into the eCRFs with the source documents (eg, hospital/clinic/physician's office medical records); a sample may be reviewed. The nature and location of all source documents will be identified to ensure that all sources of original data required to complete the eCRF are known to the sponsor and study-site personnel and are accessible for verification by the sponsor study-site contact. If electronic records are maintained at the study site, the method of verification must be discussed with the study-site personnel.

Direct access to source documents (medical records) must be allowed for the purpose of verifying that the recorded data are consistent with the original source data. Findings from this review will be discussed with the study-site personnel. The sponsor expects that, during monitoring visits, the relevant study-site personnel will be available, the source documents will be accessible, and a suitable environment will be provided for review of study-related documents. The monitor will meet with the investigator on a regular basis during the study to provide feedback on the study conduct.

In addition to on-site monitoring visits, remote contacts can occur. It is expected that during these remote contacts, study-site personnel will be available to provide an update on the progress of the study at the site. Central monitoring will take place for data identified by the sponsor as requiring central review.

17.9. Study Completion/Termination

17.9.1. Study Completion/End of Study

The study is considered completed with the last scheduled study contact shown in the Time and Events Schedule for the last subject participating in the study. The final data from the study site will be sent to the sponsor (or designee) after completion of the final subject study contact at that study site, in the time frame specified in the Clinical Trial Agreement.

17.9.2. Study Termination

The sponsor reserves the right to close the study site or terminate the study at any time for any reason at the sole discretion of the sponsor. Study sites will be closed upon study completion. A study site is considered closed when all required documents and study supplies have been collected and a study-site closure visit has been performed.

The investigator may initiate study-site closure at any time, provided there is reasonable cause and sufficient notice is given in advance of the intended termination.

Reasons for the early closure of a study site by the sponsor or investigator may include but are not limited to:

- Failure of the investigator to comply with the protocol, the requirements of the IEC/IRB or local health authorities, the sponsor's procedures, or GCP guidelines
- Inadequate recruitment of subjects by the investigator
- Discontinuation of further study drug development

17.10. On-Site Audits

Representatives of the sponsor's clinical quality assurance department may visit the study site at any time during or after completion of the study to conduct an audit of the study in compliance with regulatory guidelines and company policy. These audits will require access to all study records, including source documents, for inspection. Subject privacy must, however, be respected. The investigator and study-site personnel are responsible for being present and available for consultation during routinely scheduled study-site audit visits conducted by the sponsor or its designees.

Similar auditing procedures may also be conducted by agents of any regulatory body, either as part of a national GCP compliance program or to review the results of this study in support of a regulatory submission. The investigator should immediately notify the sponsor if he or she has been contacted by a regulatory agency concerning an upcoming inspection.

17.11. Use of Information and Publication

All information, including but not limited to information regarding rivaroxaban or the sponsor's operations (eg, patent application, formulas, manufacturing processes, basic scientific data, prior clinical data, formulation information) supplied by the sponsor to the investigator and not previously published, and any data, including research data, generated as a result of this study, are considered confidential and remain the sole property of the sponsor. The investigator agrees to maintain this information in confidence and use this information only to accomplish this study, and will not use it for other purposes without the sponsor's prior written consent.

The investigator understands that the information developed in the study will be used by the sponsor in connection with the continued development of rivaroxaban, and thus may be disclosed as required to other clinical investigators or regulatory agencies. To permit the information derived from the clinical studies to be used, the investigator is obligated to provide the sponsor with all data obtained in the study.

The results of the study will be reported in a Clinical Study Report generated by the sponsor and will contain data from all study sites that participated in the study as per protocol. Recruitment performance or specific expertise related to the nature and the key assessment parameters of the study will be used to determine a coordinating investigator. Results of analyses performed after

the Clinical Study Report has been issued will be reported in a separate report and will not require a revision of the Clinical Study Report. Study subject identifiers will not be used in publication of results. Any work created in connection with performance of the study and contained in the data that can benefit from copyright protection (except any publication by the investigator as provided for below) shall be the property of the sponsor as author and owner of copyright in such work.

Consistent with Good Publication Practices and International Committee of Medical Journal Editors guidelines, the sponsor shall have the right to publish such primary (multicenter) data and information without approval from the investigator. The investigator has the right to publish study site-specific data after the primary data are published. If an investigator wishes to publish information from the study, a copy of the manuscript must be provided to the sponsor for review at least 60 days before submission for publication or presentation. Expedited reviews will be arranged for abstracts, poster presentations, or other materials. If requested by the sponsor in writing, the investigator will withhold such publication for up to an additional 60 days to allow for filing of a patent application. In the event that issues arise regarding scientific integrity or regulatory compliance, the sponsor will review these issues with the investigator. The sponsor will not mandate modifications to scientific content and does not have the right to suppress information. For multicenter study designs and substudy approaches, secondary results generally should not be published before the primary endpoints of a study have been published. Similarly, investigators will recognize the integrity of a multicenter study by not submitting for publication data derived from the individual study site until the combined results from the completed study have been submitted for publication, within 12 months of the availability of the final data (tables, listings, graphs), or the sponsor confirms there will be no multicenter study publication. Authorship of publications resulting from this study will be based on the guidelines on authorship, such as those described in the Uniform Requirements for Manuscripts Submitted to Biomedical Journals, which state that the named authors must have made a significant contribution to the design of the study or analysis and interpretation of the data, provided critical review of the paper, and given final approval of the final version.

Registration of Clinical Studies and Disclosure of Results

The sponsor will register and disclose the existence of and the results of clinical studies as required by law.

REFERENCES

1. Attard C1, Monagle P, Kubitzka D, Ignjatovic V. The in vitro anticoagulant effect of rivaroxaban in children. *Thromb Res.* 2012 Nov;130:804-807.

Attachment 1: Volume of Blood to be Collected

Volume of Blood to be Collected From Each Subject

| Type of Sample | Volume per Sample (mL) | No. of Samples per Subject Part A/Part B | Total Volume of Blood (mL) ^a Part A/Part B |
|--------------------------------------|------------------------|--|---|
| Safety Labs | | | |
| - Hematology ^b | 1.2 | 2/2 | 2.4/2.4 |
| - Serum chemistry ^c | 1.1 | 3/2 | 3.3/2.2 |
| - Baseline PT, aPTT | 1.4 | 1/0 | 1.4/0 |
| Pharmacokinetic samples | 0.6 | 10/6 | 6.0/3.6 |
| PD-1: PD samples (PT and aPTT tests) | 1.4 | 10/7 | 14/9.8 |
| PD-2: PD samples (anti-FXa assay) | 1.4 | 4/5 | 5.6/7.0 |
| Approximate Total | | | 32.7/25 |

ALT= alanine aminotransferase; aPTT= activated partial thromboplastin time; AST= aspartate aminotransferase; CBC= complete blood count; FXa=Factor Xa; No.= number; PD= pharmacodynamics; PT= prothrombin time.

- a. Calculated as number of samples multiplied by amount of blood per sample.
- b. CBC with differential, platelet count;
- c. Liver function tests (ALT, AST, total and direct bilirubin, alkaline phosphatase) and creatinine.

Notes:

Repeat or unscheduled samples may be taken for safety reasons or technical issues with the samples.
An indwelling intravenous cannula is recommended for blood sample collection.
Blood discarded due to blood drawing from peripheral or central lines are not included in this table.

Attachment 2: Post-Fontan Echocardiographic Examination protocol

Boston Children's Hospital: Echocardiographic Examination Protocol (Please see Technical Reference Manual for further details)

Status Post Fontan Operation

Inclusion: Patient having undergone a Fontan operation. This operation has been performed with various surgical modifications including: 1) direct anastomosis of the right atrium to the pulmonary artery; 2) valved or non-valved conduit from right atrium to right ventricle; 3) classic Glenn shunt (superior vena cava to transected right pulmonary artery) and conduit from inferior vena cava to left pulmonary artery; 4) bidirectional Glenn shunt plus intra-atrial conduit connection from the inferior vena cava to the right pulmonary artery; 5) bidirectional Glenn shunt plus extracardiac conduit connection from the inferior vena cava to the main pulmonary artery. **Optimal evaluation of the Fontan is achieved by knowledge of the specific type of connection that was performed. The individual performing the examination must find out the details of the operation before the examination.**

Blood pressure in arm and leg if status post Norwood or arch reconstruction.

Full examination of anatomy using 2D, color and spectral Doppler and 3-D evaluation when indicated.

Particular attention should be given to the following:

Subcostal

- The inferior vena cava (IVC) and intracardiac portion of Fontan with 2D, color, and pulsed Doppler. Visualization of Fontan fenestration and if present, pulsed Doppler with mean gradient measured
- Baffle leak
- Atrial septal defect (ASD) (pulmonary vein to atrioventricular [AV] valve pathway), rule out obstruction or restriction along entire pathway including pulmonary veins. If 2D or Doppler evidence of restriction, obtain mean gradient
- Rule out thrombus

Apical

- Fontan fenestration with pulsed Doppler and mean gradient
- Baffle leak
- Atrial Septal Defect (pulmonary vein to AV valve pathway) to exclude restriction. If 2D or Doppler evidence of restriction, obtain mean gradient.
- Atrioventricular valve regurgitation
- Aortic and/or pulmonary valve if present, including pulsed wave and continuous wave Doppler of outflow and assessment of regurgitation jet
- Rule out thrombus

Parasternal

- Aortic and/or pulmonary valve for regurgitation
- Aortic, neoaortic and ascending aorta measurements
- Assess for main pulmonary artery stump and any thrombus
- Assess a hypoplastic aortic root for flow, rule out thrombus
- Branch pulmonary arteries with 2D measurements, color, and pulsed Doppler
- Baffle in parasternal short axis, and long axis. Assess for thrombus
- Assess for pulmonary vein obstruction

Suprasternal

- Glenn shunt (superior vena cava down to cavopulmonary anastomosis if possible) with 2D and with color (color compare) and pulsed Doppler
- Branch pulmonary arteries with 2D measurements, color and pulsed Doppler
- Aortic arch

Full function protocol (systolic and diastolic) regardless of ventricular morphology

Attachment 3: Estimated glomerular filtration rate (eGFR)

- The original Schwartz formula: If serum creatinine (SCr) is measured with routine methods that have not been recalibrated to be traceable to isotope dilution mass spectrometry (IDMS) (eg, the traditional Jaffé reaction), the estimated glomerular filtration rate (eGFR) should be obtained from the original Schwartz formula:²⁸

$eGFR \text{ (mL/min/1.73 m}^2\text{)} = k * \text{height (cm)} / \text{SCr g/dL}$ where k is proportionality constant:

k = 0.55 in children up to 13 years

- The updated Schwartz formula: If SCr is measured by an enzymatic creatinine method that has been calibrated to be traceable to IDMS, the updated Schwartz formula should be used to obtain the eGFR:²⁹

$eGFR \text{ (mL/min/1.73 m}^2\text{)} = 0.413 * \text{height (cm)} / \text{SCr mg/dL}$

The National Kidney Disease Education Program website

(http://www.nkdep.nih.gov/professionals/gfr_calculators/index.htm) offers electronic calculators of eGFR in the pediatric population based on the updated Schwartz formula. Serum creatinine in micromoles per liter, the value should be multiplied by 88.4 (1 mg/dL = 88.4 umol/L).

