4. SUBJECT POPULATION

Screening for eligible subjects will be performed within 21 days before administration of the study drug.

The inclusion and exclusion criteria for enrolling subjects in this study are described in the following 2 subsections. If there is a question about the inclusion or exclusion criteria below, the investigator must consult with the appropriate sponsor representative and resolve any issues before enrolling a subject in the study. Waivers are not allowed.

For a discussion of the statistical considerations of subject selection, refer to Section 11.2, Sample Size Determination.

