4.2. Exclusion Criteria

Any potential subject who meets any of the following criteria will be excluded from participating in the study.

1. Evidence of thrombosis, including those that are asymptomatic confirmed by post-Fontan procedure transthoracic echocardiogram, or other imaging techniques, during the screening period of the study
2. History of gastrointestinal disease or surgery associated with clinically relevant impaired absorption
3. History of or signs/symptoms suggestive of protein-losing enteropathy
4. Active bleeding or high risk for bleeding contraindicating antiplatelet or anticoagulant therapy, including a history of intracranial bleeding
5. Criterion modified per Amendment INT-2
 - 5.1. Indication for anticoagulant or antiplatelet therapy other than current study, however:
 - A subject who has received VKA after the Fontan procedure may be eligible provided that the subject has discontinued VKA before the screening visit. Baseline laboratory samples must be obtained at least 7 days after the last dose of VKA.
 - A subject who is receiving ASA at the time of the screening visit may be eligible and may continue on ASA provided the last dose is taken at least 24 hours prior to the first dose of study drug.
 - A subject who is receiving heparin or LMWH after the Fontan procedure may be eligible and may continue receiving either of these anticoagulants during the screening period provided the study drug (rivaroxaban or ASA) is started 0 to 2 hours prior to the next scheduled administration of either of these anticoagulants and omit their administration thereafter.
6. Chronic use of NSAIDs
7. Platelet count $<50 \times 10^9/L$ at screening
8. Criterion modified per Amendment INT-2

-
- 8.1. Estimated glomerular filtration rate (eGFR) $<30 \text{ mL/min/1.73m}^2$ (Attachment 3)
 9. Known clinically significant liver disease (eg, cirrhosis, acute hepatitis, chronic active hepatitis, or alanine aminotransferase (ALT) $>3x$ upper limit of normal (ULN) with concurrent total bilirubin $>1.5x$ ULN with direct bilirubin $>20\%$ of the total at screening)
 10. Criterion modified per Amendment INT-2
 - 10.1. Known contraindication to ASA, or has or is recovering from chicken pox or flu-like symptoms (subjects participating in Part B only)
 11. Criterion modified per Amendment INT-2
 - 11.1. Known allergies, hypersensitivity, or intolerance to rivaroxaban, ASA or its excipients (Investigator's Brochure)¹⁴
 12. Inability to cooperate with study procedures

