9.3.3. Other Safety Assessments

The safety and tolerability of rivaroxaban will also be evaluated by assessing other adverse events and clinical laboratory test values.

Any clinically relevant changes, including laboratory reports, occurring during the study must be recorded on the Adverse Event section of the eCRF. Any clinically significant abnormalities persisting at the end of the study/early withdrawal will be followed by the investigator until resolution or until a clinically stable endpoint is reached.

The study includes the evaluations of safety and tolerability according to the time points provided in the Time and Events Schedule.

Adverse Events

Adverse events will be reported by the parents/legally acceptable representatives for the duration of the study up to the Follow-Up Contact (30-days after last dose). Adverse events will be followed by the investigator as specified in Section 12, Adverse Event Reporting.

Clinical Laboratory Tests

The following tests results with reference ranges will be obtained at the visits specified in the Time and Events Schedule. Either hospital laboratory/local laboratory results or central laboratory results are acceptable at the time of study screening period. A central laboratory will be used during the rest of the study:

- Hematology Panel
 - hemoglobin
 - hematocrit
 - red blood cell (RBC) count^a
 - white blood cell (WBC)^b count
 - WBC differential^b:
 - neutrophils
 - lymphocytes
 - monocytes
 - eosinophils
 - basophils
 - platelet count
- Serum chemistry
 - creatinine (eGFR will be calculated using the original or the modified Schwartz formula for pediatric population, see [Attachment 3](#))²⁹
 - liver function tests (ALT, aspartate aminotransferase [AST], total and direct bilirubin, alkaline phosphatase)
- PT, aPTT tests

^a A RBC evaluation may include abnormalities in RBC count and/or RBC parameters (eg, reticulocyte count) and/or RBC morphology, which will then be reported by the laboratory

^b A WBC evaluation may include any abnormal cells, which will then be reported by the laboratory. In addition, any other abnormal cells in a blood smear will also be reported.

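### Attachment 3 shows creatinine in g/dL for the original Schwartz formula but mg/dL for the updated one (check the PDF for a lost 'm'), and its micromol/L sentence omits the step a site needs

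*Protocol*

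**What the plan says.** Protocol Section 4.2 opens by stating: "Any potential subject who meets any of the following criteria will be excluded from participating in the study". Criterion 8.1 in that list is an eGFR below 30 mL/min/1.73 m², with a reference to Attachment 3. Section 9.3.3 points to the same attachment: "creatinine (eGFR will be calculated using the original or the modified Schwartz formula for pediatric population". For the source of the creatinine value, it says: "Either hospital laboratory/local laboratory results or central laboratory results are acceptable at the time of study screening period".

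Attachment 3 gives two formulas, chosen by assay type:

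- Original Schwartz, for assays not traceable to IDMS: k times height in cm, divided by creatinine, with k = 0.55. The text reads "SCr g/dL}$ where k is proportionality constant". The stray typesetting characters come from text extraction.
- Updated Schwartz, for IDMS-traceable enzymatic assays: 0.413 times height in cm, divided by creatinine in mg/dL.

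Both return mL/min/1.73 m². The attachment then cites a website that "offers electronic calculators of eGFR in the pediatric population based on the updated Schwartz formula" and ends with: "Serum creatinine in micromoles per liter, the value should be multiplied by 88.4 (1 mg/dL = 88.4 umol/L", followed by the closing bracket.

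**The concern.** An exclusion criterion needs a formula that a site can apply as printed. Here the two formulas take creatinine in units 1,000-fold apart, although their constants are close and their other units are identical. No other passage in the protocol or SAP states the creatinine unit. Because hospital and local laboratory results are accepted at screening, assay type and reporting unit can vary by site, and a site may have to do the calculation itself.

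The closing sentence does not repair this. It lacks an opening clause, does not say which value is multiplied, and does not name the resulting unit. A site whose laboratory reports micromol/L is not told how to obtain the mg/dL value.

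What is at stake is whether 8.1 works as written. Protocol Section 6 also relies on that exclusion when it explains why the dosing scheme makes no allowance for renal impairment. This point does not comment on the dosing rule itself.

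**Working it through.** **Inputs from Protocol Attachment 3 and criterion 8.1:** constants 0.55 and 0.413; threshold 30; identity 1 mg/dL = 88.4 micromol/L. **Assumptions, not in the documents:** height 100 cm (range 80 to 130 cm); illustrative creatinine values of 2.5 mg/dL and 40 micromol/L. The documents print no worked eGFR example, so there is no stated figure to reproduce.

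**1. Consistency of the two formulas.** Ratio of constants: 0.55 / 0.413 = 1.332. Ratio of creatinine units as shown: 1 g/dL / 1 mg/dL = 1,000. With the same height and output units, both cannot be right. The updated formula and the conversion identity both use mg/dL, so g/dL is the odd one out.

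**2. Creatinine at which 8.1 applies** (constant × height / 30).

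| Height (assumed) | Original, as shown (g/dL) | Same, in mg/dL | Original, if mg/dL is meant | Updated, as shown |
|---|---|---|---|---|
| 80 cm | 0.55 × 80 / 30 = 1.467 | 1,467 | 1.47 mg/dL | 0.413 × 80 / 30 = 1.10 mg/dL |
| 100 cm | 0.55 × 100 / 30 = 1.833 | 1,833 | 1.83 mg/dL | 0.413 × 100 / 30 = 1.38 mg/dL |
| 130 cm | 0.55 × 130 / 30 = 2.383 | 2,383 | 2.38 mg/dL | 0.413 × 130 / 30 = 1.79 mg/dL |

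The updated cut-off at 100 cm is 1.377 × 88.4 = 122 micromol/L (97 to 158 over the height range).

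**3. One child, original formula**, 100 cm and 2.5 mg/dL (0.0025 g/dL):

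- as shown: 0.55 × 100 / 0.0025 = 22,000, not excluded;
- with mg/dL: 0.55 × 100 / 2.5 = 22, excluded.

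**4. The conversion sentence**, updated formula, 100 cm and 40 micromol/L:

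- divide creatinine by 88.4 before use: 0.413 × 100 / (40 / 88.4) = 91.3, correct;
- enter micromol/L, then multiply the resulting eGFR by 88.4: (0.413 × 100 / 40) × 88.4 = 1.0325 × 88.4 = 91.3, also correct, but a strained reading because the sentence is about creatinine;
- take the sentence as converting mg/dL to micromol/L (the conversion itself is correct) and enter the micromol/L value: 0.413 × 100 / 40 = 1.03, wrong;
- multiply the micromol/L creatinine by 88.4 before entry: 0.413 × 100 / (40 × 88.4) = 0.012, wrong.

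The one step that makes a micromol/L result usable in either formula, dividing by 88.4, is not stated as an instruction.

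**The case against.** The strongest reply is that the unit conflict may not be in the protocol at all. It rests on one letter in an equation read by machine, and a lost 'm' cannot be excluded from the extracted text. That stands: the unit part depends on the PDF. The conversion sentence is a separate matter and would remain if the PDF shows mg/dL.

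Second, the conversion sentence carries its own direction. With the identity beside it, the natural reading is that mg/dL times 88.4 gives micromol/L, which is correct. A reader might infer that the attachment tells sites to convert the wrong way. It does not: the identity argues against multiplying a micromol/L value. What stands against the sentence is narrower. It yields a unit that neither formula is shown to take, and it leaves out the step in the other direction.

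Third, the errors would show themselves. An eGFR in the tens of thousands, or of 1 or less in a clinically stable child, would hardly pass unnoticed. The intended unit appears twice in the same attachment. Section 4 adds: "If there is a question about the inclusion or exclusion criteria below, the investigator must consult with the appropriate sponsor representative", and requires the issue to be resolved before enrolment. Exclusion 17 also gives the investigator separate discretion. All this stands and keeps the severity low. One limit applies: the calculators the attachment mentions are for the updated formula only, so the formula with the suspect unit has no such backup.

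**Conclusion.** The point holds in two parts, both minor. Subject to the PDF check, the creatinine unit in the original Schwartz formula is wrong by a factor of 1,000. Followed literally, that formula could not exclude any child under 8.1, since it would need creatinine above about 1,833 mg/dL at 100 cm (1,467 to 2,383 for 80 to 130 cm; heights assumed). Independently of the PDF check, the micromol/L sentence is incomplete and does not give the conversion a site needs. The updated formula with creatinine in mg/dL is usable as printed.

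A reader might go further and infer that children below the threshold were enrolled, or that the trial's results are affected. The documents do not support either. Nothing in them shows a miscalculated eGFR. The main efficacy description (SAP Section 5) uses the Full Analysis Set, less children whose screening echocardiogram was centrally read as showing thrombosis. The main bleeding description (SAP Section 4.1) uses the Safety Analysis Set. Neither depends on 8.1. Only the Per-protocol Set (SAP Section 2.2) does, and SAP Section 5 makes its summary optional.

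Nor do the documents support a retrospective recalculation of eGFR. No misclassification is alleged, and deciding which children to include would rest on amendment logs that describe superseded text.

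**What to change.** Check the original Schwartz equation against the PDF. Then make two edits in Attachment 3:

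1. Print 'SCr mg/dL' in both formulas.
2. Replace the last sentence with: *If serum creatinine is reported in micromol/L, divide by 88.4 to obtain mg/dL before use.*

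The cost is two lines in one attachment. The eGFR threshold, the choice of formula by assay type, the analysis sets and the analyses all stay as they are. If the PDF already prints mg/dL in the original formula, only the second edit is needed.
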